8. REGULATORY ISSUES

8.1 ETHICS APPROVAL

The Chief Investigator has applied for approval from the Research Ethics Committee and Health Research Authority (HRA) approval. The study will be submitted to each proposed research site for Confirmation of Capacity and Capability. The study will be conducted in accordance with the recommendations for physicians involved in research on human subjects adopted by the 18th World Medical Assembly, Helsinki 1964 and later revisions.

8.2 CONSENT

Consent to enter the study must be sought from each participant only after a full explanation has been given, an information leaflet offered and time allowed for consideration. Signed participant consent should be obtained. The right of the participant to refuse to participate without giving reasons must be respected. After the participant has entered the study the clinician remains free to give alternative treatment to that specified in the protocol at any stage if he/she feels it is in the participant's best interest, but the reasons for doing so should be recorded. In these cases the participants remain within the study for the purposes of follow-up and data analysis. All participants are free to withdraw at any time from the protocol treatment without giving reasons and without prejudicing further treatment.

8.3 CONFIDENTIALITY

The Chief Investigator will preserve the confidentiality of participants taking part in the study and will abide by the Data Protection Act. Each scan performed has a unique patient identifier and will be requisite to retrieve the scan images. However, this will be mapped to a pseudonymised code that won't immediately identify the patient's scan instance. To avoid 'losing' scan instances through incorrect patient identifiers, the patient's hospital number will additionally be noted. Each scan will be anonymised and once the abdominal wall depth has been measured and associated to the respective patient's physical measurement with the patient being identified through a code, we will no longer need the hospital number and will instead use the pseudonymised code. Data such as age, gender & ethnicity will also be collected and not shared to any party outside of the research group. This data will be stored in a password restricted university laptop and the measures in place to store data in a secure fashion will follow general data protection regulations. It will not be possible to identify individual participants from the data linked to the pseudonymised code and only the research personnel will have access to this data. Person identifiable data will not be required. The physical measurement data will be retained for 10 years and destroyed thereafter. It will be retained securely should it be required for future use.

8.4 INDEMNITY

There are no requirements for arrangements for extra indemnity cover. This owes to the fact that there are no significant risks posed to any participants or researchers in this study and also that Liverpool Women's Hospital NHS Foundation Trust has agreed to act as sponsor of this project.

8.5 SPONSOR

The Liverpool Women's NHS Foundation Trust will act as the Sponsor for this study.

8.6 FUNDING

CDT Digital Health are funding this study. No participant or investigator payments will be effected.

8.7 AUDITS

The study may be subject to inspection and audit by the Sponsor and other regulatory bodies to ensure adherence to GCP and the UK Policy Framework for Health and Social Care Research.

9. STUDY MANAGEMENT

The day-to-day management of the study will be coordinated through [contact]

10. END OF STUDY

Data linkage for all recruited participants

11. ARCHIVING

Data and all appropriate documentation will be stored for a minimum of 5 years after the completion of the study.

12. PUBLICATION POLICY

The results of this study will be published in a peer reviewed journal

14. APPENDICES

14.1 Principal Investigator responsibilities

The PI will attend the initiation meeting (already done) and ensure all members of the trial team are familiarised in the protocol and its procedures, attend to recruit patients at the point of their radiology attendance, enter all physical measurement data in the secure data sheet and correspond these to the respective scan image of the patient from which the abdominal wall depth will be calculated. Furthermore the PI will disseminate important safety or trial related information to all stakeholders within their site where required, safety report any incidents (highly unlikely) within the timelines and complete all study documentation.

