1.2 RATIONALE FOR CURRENT STUDY

This study seeks to assess whether the waist circumference can estimate the abdominal wall depth to a reliable degree of accuracy so as to be incorporated in a nomogram that would categorise suggested Veres needle abdominal insertion depth according to waist circumference range.

The research question is therefore 'Can the waist circumference be employed as an estimate of the abdominal wall depth?'

This would be helpful in guiding initial Veres entry into the abdominal cavity during laparoscopic (key-hole) or robotic surgery where entry is achieved blind without standardised depth advice. The traditional Body Mass Index (BMI) will also be taken to see if it makes a better correlation than abdominal girth. A study has previously been carried out analysing the relationship between BMI and vertical distance between umbilicus and retroperitoneal vessels (1) but we hypothesise waist circumference may be a better measure. The abdominal wall depth will be measured directly from abdominal Computed Tomography (CT) or Magnetic Resonance Imaging (MRI) scans with the waist, weight and height measurements to be physically taken from eligible consenting participants. The existence of a relationship that can be reliable in guiding needle depth investigation is hypothesised and requires further investigation.

Due to urgent need for safety mechanisms to be incorporated in the conduct of laparoscopic abdominal wall injury, this study attempts to provide some guidance into how deep the Veres needle should be inserted when a Veres needle is being used as the first entry abdominal device and insufflator. The study is aiming to improve safety in laparoscopic entry where a Veres needle is used by providing insertion depth guidance. It is aimed to reduce the number of failed entries or complicated entries.

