2. STUDY OBJECTIVES

2.1 Primary Objectives

- 2.11. Investigate the correlation between waist circumference and abdominal wall depth through physical data collection. Waist circumferences will be obtained from patients as actual physical measurements and not estimated while the abdominal wall depth will be ascertained from each patient's corresponding cross sectional image.
- 2.12 Measure the abdominal wall depth of each participant from their cross sectional image. During laparoscopy, patients are in the same supine position and with patients required to be still during their scan, a reliable depth measurement can be taken as a proxy for their actual abdominal wall depth.

Produce descriptive statistics of the depths in the cohort of patients. Group each 1cm of abdominal wall depths by categories of waist circumference

2.13. Produce a nomogram for use as a predictor of abdominal wall depth.

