4. PARTICIPANT ENTRY

Participants undergoing routine abdominal or pelvic CT scans will have their waist circumference measured immediately prior to the scan commencing upon appropriate positioning. The weight and height are routinely collected physical measurements on arrival.

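### Sections 14.1 and 8.3 do not clearly agree on whether wall depth is read before or after the scan is linked to the waist value, and neither masks the depth reader

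*Protocol*

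**What the plan says.** The waist is taken first. Section 4 says that participants "will have their waist circumference measured immediately prior to the scan commencing". The schedule of events (14.4) places the depth calculation later, under scan post-processing. Section 2.1 takes depth from the image: "the abdominal wall depth will be ascertained from each patient's corresponding cross sectional image".

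Two sections describe how the measurements and the scan come together:

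- Section 14.1 gives the principal investigator the tasks of recruitment and data entry ("enter all physical measurement data in the secure data sheet"). The same sentence then adds a matching step: "correspond these to the respective scan image of the patient from which the abdominal wall depth will be calculated".
- Section 8.3 gives this sequence: "Each scan will be anonymised and once the abdominal wall depth has been measured and associated to the respective". It goes on to say that, after this link to the body measurements is made, a pseudonymised code replaces the hospital number.

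Section 8.3 limits data access to the research personnel as a group. No section names the depth reader, separates the reader from the person who measured the waist, or says what the reader may see. Section 1.2 records the team's expectation when comparing waist with BMI: "we hypothesise waist circumference may be a better measure".

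**The concern.** Depth is the single outcome behind the primary objective ("Investigate the correlation between waist circumference and abdominal wall depth through physical data collection"), the correlation equation and the nomogram. Placing two measuring points on an image involves some judgement. This document gives no rule for slice level or end points beyond measurement from the belly button, though one may exist elsewhere.

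The waist value always exists before depth is read, and under 14.1 one role holds it and matches it to the scan. Followed as written, the protocol allows the outcome to be read with the predictor known. A reader who expects larger waists to go with deeper walls may, without intending to, settle borderline readings in that direction. Such error follows the predictor, so a larger sample does not average it out.

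The nomogram is meant to inform a blind needle entry, so limits that look tighter than they are would matter. Who reads the outcome, and with what knowledge, is study conduct. An analysis plan written later cannot mask readings already taken.

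**Working it through.** **1. The order of work, section by section**

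- Section 14.1: enter the measurements, match them to the scan, and depth *will be* calculated from that scan. The future tense suggests matching before reading. The clause may instead only identify which image is meant.
- Section 8.3: the scan is anonymised, and depth is measured and associated with the measurements. Taken in the order listed, reading precedes association.
- Masking: 8.3 hides identity. It says nothing about withholding waist, weight or height, and the hospital number stays in use until depth has been measured and associated. Section 14.1 says nothing on masking.

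So the two sections do not clearly agree on order, and neither masks the reader.

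**2. The plan's own figure**

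The only relevant number is the sample size in section 7. With z = 1.96, an assumed proportion of 0.5, and the stated 5% read as a margin of error, z² × 0.25 / 0.05² is about 384.1, rounded up to 385. It reproduces. It has no bearing on masking and is used below only for the scale of sampling error.

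**3. Illustration A: shading proportional to waist**

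The protocol gives no depth SD, expected correlation, reading error or size of reader bias, so all of these are assumed. Let waist be standardised, r the true correlation, and s the shading per waist SD divided by the depth SD. Then

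r′ = (r + s) / √[(r + s)² + 1 − r²]

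| True r | Depth SD | Shading per waist SD | s | r′ |
|---|---|---|---|---|
| 0.50 | 1 cm | 0.5 mm | 0.05 | 0.55/√(0.3025 + 0.75) = 0.536 |
| 0.50 | 1 cm | 1 mm | 0.10 | 0.60/√(0.36 + 0.75) = 0.569 |
| 0.50 | 2 cm | 0.5 mm | 0.025 | 0.525/√(0.2756 + 0.75) = 0.518 |
| 0.50 | 2 cm | 1 mm | 0.05 | 0.536 |
| 0.60 | 1 cm | 0.5 mm | 0.05 | 0.65/√(0.4225 + 0.64) = 0.631 |
| 0.60 | 1 cm | 1 mm | 0.10 | 0.70/√(0.49 + 0.64) = 0.659 |

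For scale, SE(r) ≈ (1 − r²)/√384, which is 0.75/19.6 = 0.038 at r = 0.50 and 0.64/19.6 = 0.033 at r = 0.60. From r = 0.50, the shift is about 0.9 SE (0.5 mm) or 1.8 SE (1 mm) with a depth SD of 1 cm, and about 0.5 or 0.9 SE with a depth SD of 2 cm.

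In this model the standardised slope rises from r to r + s, for example from 0.50 to 0.60, and the residual scatter is unchanged.

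**4. Illustration B: readings pulled toward the predicted depth**

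If each reading moves a fraction L toward the depth predicted from waist,

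r′ = r / √[r² + (1 − L)²(1 − r²)]

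| True r | L = 5% | L = 10% | L = 20% |
|---|---|---|---|
| 0.50 | 0.519 | 0.540 | 0.585 |
| 0.60 | 0.620 | 0.640 | 0.684 |

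Here the slope is unchanged, but the residual SD shrinks by the fraction L, so nomogram limits would look too narrow by that fraction. Both forms raise the correlation. They differ in what else they distort.

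**The case against.** The strongest reply is that the protocol describes no unmasked reading. A reader might infer from 14.1 that depth is always read after linkage. The text does not support that: it is a list of duties, it does not name the depth reader, and 8.3 points the other way. Nor does any section say that the reader is shown the waist value. A code that could lead to the data sheet is not the same as having the sheet open. These points stand. What remains is that the protocol permits such a reading and does not settle the order.

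A reader might also infer that 8.3 has to be reversed. It does not: it already lists measurement before association. What it lacks is a statement that the reader has no access to the measurements.

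A third tempting inference is that the bias would favour waist over BMI in objective 2.21. This is not shown. The same sheet holds weight and height, so shading toward general body size could raise both correlations. The stated expectation is also tentative: waist *may be* better.

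Finally, the image itself shows girth, so masking can only be partial. That is true and limits the benefit. The illustrations describe total shading, not the part that hiding the recorded number would prevent. Still, an impression of size from an image is less exact than a recorded circumference, and withholding the number costs almost nothing.

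**Conclusion.** The point holds as an unresolved order of work together with an unmasked outcome reading. It is not a demonstrated bias. Sections 14.1 and 8.3 need to be reconciled, because as they stand the sole outcome can be read with the predictor known.

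If that happened, the correlation would be inflated, and the slope or the apparent nomogram precision distorted. The size is unknown. The illustration, from 0.50 to between 0.52 and 0.57 over 0.5 to 1 mm of shading and a depth SD of 1 to 2 cm, rests wholly on assumed inputs. It also assumes shading exactly linear in waist, which favours inflation. At most it reaches about two standard errors of the correlation at 385 participants, and over much of the range it is one or less.

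It would be too strong to call the bias beyond detection: a masked re-read of a sample of coded scans could measure it. Preventing it is simpler.

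**What to change.** Reconcile 14.1 with 8.3 in one paragraph that states:

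- scans are exported under the pseudonymised code;
- depth is read in batches and in random order, with the physical-measurement sheet closed, and entered in a separate file;
- the depth file is locked before linkage;
- waist, weight and height are linked by code only after that.

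Reword 14.1 so that the investigator's matching step comes after the lock. In 8.3, keep the existing order and add that the reader has no access to the measurements. State in the report that masking is partial because the image shows body size.

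The cost is the wording and a changed order of work: depth can no longer be entered at the same sitting as the waist. No extra reader, scan or patient is needed.

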14.2 Required documentation

14.21 CV of the Chief Investigator [name] attached in IRAS Project Form

14.22 Metric measurements

Units of measurements (metric)				
Waist circumference	cm			
Weight	kg			
Height	cm			
Abdominal wall depth	cm			

14.3 Expected Side Effects

None anticipated as the data to be obtained from patients is simply height, weight and waist circumference.

14.4 Schedule of events Excel Table

Radiology Study	PI: [name] Study Short Name: Waist circumference as an estimator of abdominal wall depth							
Schedule Of Events:								
Study Item, Service, or Activity	Screening	Imaging day	Scan Post Processing				Comments	Footnotes
Patient identification & selection with radiology								
appointments department	Х							non-urgent imaging only
Inclusion / Exclusion Criteria	х							
Participant Information Sheet given & Consent Signed	х	х						
Physical Exam		х						*end of participant physical involvement in the study
Abdominal wall depth calculation			Х	_			·	Weight, Height, Waist circumference at Screening visit.
End of Study on achievement of sample size
